13.1.4 Safety Analyses

All safety data analyses will be performed using the SAF. Summaries will be provided for each trial arm and overall.

Solicited AEs

Solicited AEs will be assessed during 30 minutes after administration of each dose of trial vaccine and then daily for 7 days (including the day of administration). For each solicited AE, the number and percentage of subjects will be computed, for each day from Day 1 to Day 7 after each trial vaccine dose administration (including the day of trial vaccine administration) and overall.

Solicited AEs will be summarized by intensity and, for systemic events, by relationship to the trial vaccine. For subjects with more than 1 episode of the same event within an interval, the maximum intensity and strongest relationship will be used for tabulations.

Body temperature measurements will be summarized in categories (including fever, defined as temperature $\geq 38^{\circ}\text{C}$), without adjustment for the route of measurement. Summaries of the day of first onset of each event and the number of days subjects experienced each event will also be provided.

Data from the 30 minutes assessment will be summarized separately.

Unsolicited AEs

Any unsolicited AEs, SAEs, MAAEs, and AEs leading to trial vaccine or trial withdrawal, will be coded using MedDRA, and summarized by system organ class (SOC) and preferred term (PT) using number and percentage of subject with an AE. Subjects with more than one occurrence for the term will be counted only once for this term.

For any unsolicited AEs, collected up to 28 days after administration of each dose of trial vaccine (including the day of administration), summaries will also be provided by event intensity (mild, moderate, severe) and relationship (not related, related) to trial vaccine or trial procedures. For subjects with more than one AE within a SOC or PT, then the AE with the maximum intensity or strongest relationship within each SOC and each PT will be included in the summaries by intensity or relationship, respectively.

Any unsolicited AEs will be summarized in the following 3 time intervals: 1) overall up to 28 days after trial vaccine administration, 2) with onset between 1 and 7 days after each dose

(including the day of trial vaccine administration), and 3) with onset between 8 and 29 days after each dose (including the day of trial vaccine administration).

AEs leading to trial vaccine withdrawal

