## **9.2. Unsolicited Adverse Events**

An AE is defined as any untoward medical occurrence in a clinical investigation subject administered a trial vaccine; it does not necessarily have to have a causal relationship with trial vaccine administration. An AE can therefore be any unfavorable and unintended sign (e.g., a clinically significant abnormal laboratory finding), symptom, or disease temporally associated with the administration of a trial vaccine whether or not it is considered related to the trial vaccine.

Unsolicited AEs are collected through 28 days post-first and second vaccination. AEs leading to trial vaccine withdrawal are collected up to the second trial vaccine dose administration. SAEs, AEs leading to withdrawal from trial and MAAEs are collected for the entire study period.

The reported term for the unsolicited AE, start and end date, seriousness, severity, relationship to trial vaccine or trial procedure, action taken and outcome of event will be collected on the eCRF.

Summaries of the total number of unsolicited AEs and the number and percentage of subjects with at least one AE will be provided by trial arm. AEs will be presented by SOC and PT. At each level of subject summarization, a subject is counted once if the subject reported one or more events. Percentages will be calculated out of the number of subjects in the SAF. The summary of AEs will be presented in descending order from the SOC with the highest total incidence to the SOC with the lowest total incidence. If the total incidence for any two or more SOCs is equal, the SOCs will be presented in alphabetical order. Within each SOC, the PTs will be presented in alphabetical order.

Summaries of unsolicited AEs will be presented as follows after both vaccines (individually and combined):

1. Overall up to 28 days after trial vaccine administration;
2. With onset between Day 1 and Day 7 after each dose (including the day of trial vaccine administration);
3. With onset between Day 8 and Day 29 after each dose (including the day of trial vaccine administration).

Any AE reported between Day 29 and the second vaccination (up to Day 57) will be included in the listed.

Unsolicited AEs will be coded by PT and SOC using the latest MedDRA version.

For missing/partial start and end dates, the rules stated in Section 4 will be followed.

All AEs will be presented in a listing.

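### By-dose unsolicited AE tables: the windows overlap when dose 2 is given on Study Day 29, and SAP 4's partial-date bullets can put an onset on the wrong side of dose 2

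*SAP*

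**What the plan says.** SAP 9.2 sets the layout: "Summaries of unsolicited AEs will be presented as follows after both vaccines (individually and combined"), over three intervals. These are the whole period up to 28 days, Day 1 to Day 7, and "With onset between Day 8 and Day 29 after each dose (including the day of trial vaccine administration"). Protocol 13.1.4 has the same third interval, "with onset between 8 and 29 days after each dose (including the day of trial vaccine administration"), but describes the collection period as "collected up to 28 days after administration of each dose of trial vaccine (including the day of administration"). SAP 9.2 adds a listing-only rule: "Any AE reported between Day 29 and the second vaccination (up to Day 57) will be included in the listed". Within each table, "At each level of subject summarization, a subject is counted once if the subject reported one or more events". The AE fields begin "The reported term for the unsolicited AE, start and end date, seriousness, severity"; no onset time is named.

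The dose day is Day 1. SAP 4 adds 1 to the date difference from dose 1, Protocol 13.1.4 counts solicited events "for each day from Day 1 to Day 7 after each trial vaccine dose administration (including the day of trial vaccine administration"), and the schedule in SAP 13.2 labels 28 days after each dose as Day 29.

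The timing of dose 2 is stated in four ways: 28 to 56 days after dose 1 (Protocol 6.1), Study Day 29 to 57 (SAP 7.2), Day 28 to 56 (Protocol 9.1.6), and 29 to 56 days after dose 1 (footnote (h) in Protocol 2.3 and SAP 13.2).

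For an AE onset known only to the month, SAP 4 gives two bullets. The first uses the 1st of the month if that month is not the month of the first trial vaccination. The second uses the date of the first trial vaccine received in that month, and falls back to the 1st if this would come after the stop date. The year-only bullets are built the same way.

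**The concern.** Unsolicited AEs up to 28 days after each dose are a primary endpoint, and SAP 9.2.1 and 9.2.2 split the relationship and severity tables by vaccination. A by-dose table is read as showing what followed that dose. Two features of the text work against this.

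(a) If dose 2 is given on Study Day 29, that date is both Day 29 after dose 1 and Day 1 after dose 2. A reaction to dose 2 on the day of injection then also appears as a late event after dose 1.

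(b) A month-only onset in dose 2's month, with dose 1 in an earlier month, meets the condition of the first bullet and can also be read to fit the second. The two give different dates unless dose 2 fell on the 1st, and so can give different tables.

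**Working it through.** **Reproducing the plan's own figure.** With the SAP 4 formula, 28 + 1 = 29 and 56 + 1 = 57, which matches Study Day 29 to 57 in SAP 7.2. The 2:1 split of 21 gives 14 and 7, as stated.

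**(a) Overlap.** Dose 1's last window ends on Study Day 29. With a spacing of g days, dose 2's first window starts on Study Day g + 1. They share a day only if g + 1 ≤ 29, that is g = 28, and the shared day is Study Day 29. This is the earliest day in SAP 7.2 and the nominal Visit 2 day in SAP 13.2.

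- *Which tables.* Interval 3 is affected as written. The 28-day measure, and with it the relationship and severity tables, is affected only if the 28-day period includes Day 29. Protocol 13.1.4 can be read as Days 1–28, which gives no overlap there. Interval 3 and the listing-only rule both use Day 29.
- *Per infant.* 1/14 = 7.1 points and 1/7 = 14.3 points in a by-dose row, or 0 if the infant is already counted in that row.
- *Expected events.* Assumption, not in the documents: 0.5 to 2 unsolicited AEs per infant per 28 days, evenly spread. Expected double-tabulated onsets = (infants dosed on Day 29) × rate / 28.

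| Dose 2 timing | HIL-214 | Placebo |
|---|---|---|
| All on Day 29 | 14 × 0.5/28 = 0.25 to 14 × 2/28 = 1.0 | 7 × 0.5/28 = 0.125 to 7 × 2/28 = 0.5 |
| Spread evenly over 29 days (row above ÷ 29) | 0.009 to 0.034 | 0.004 to 0.017 |

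**(b) Month-only onsets.** Example: dose 1 on 12 June, dose 2 on 24 July (42 days later), onset recorded as July. The first bullet gives 1 July, Day 20 after dose 1. The second gives 24 July, Day 1 after dose 2.

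For the general case, take every dose 1 date in 2023 and in 2024, a spacing of 28, 42 or 56 days, and true onsets 0 to 27 days after each dose, all equally likely (dose 1 onsets only before dose 2). Keep onsets in dose 2's month when dose 1 was in an earlier month. Stop dates are ignored. Dose 2 falls in a later month for 92% of dates at 28 days and for all dates from 35 days.

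| Share of such onsets | 28 days | 42 days | 56 days |
|---|---|---|---|
| First bullet: truly after dose 2, placed before it | 52% | 74% | 94% |
| Second bullet: truly before dose 2, credited to dose 2 | 45% | 21% | 0.4% |
| First bullet: tabulated under dose 1 | 97% | 42% | 1% |
| First bullet: listing only (window ends Day 28) | 0% | 53% | 93% |
| First bullet: under dose 2 (dose 2 on the 1st) | 3% | 5% | 6% |

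With windows ending on Day 29, the first two rows become 52/72/93% and 44/23/1%. At 28 days the two error rates are similar, but the bullets still impute different dates for about 97% of these onsets.

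**The case against.** The strongest reply to (a) is that the text is not silent. Read literally, a Day 29 onset belongs in both by-dose tables and is counted once in the combined table. Neither document says that by-dose rows must be mutually exclusive, no event is lost, and the rule is the same in both arms. That stands. A reader might infer that no rule exists and that programmers must guess, or that the primary 28-day measure is double-counted. The documents support neither. The literal result is double tabulation, and the primary measure is affected only if its period includes Day 29. What remains is that the dose 1 table can carry a reaction to dose 2.

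The listing-only sentence does not settle it. It concerns AEs before a later dose 2, and it starts on a day that interval 3 still tabulates. Dosing time is collected (SAP 7.2), but onset time is not among the listed AE fields, so the order within the day cannot be derived from them. Footnote (h) would remove the overlap, but it disagrees with Protocol 6.1 and SAP 7.2.

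On (b), the second bullet may be meant as the remainder after the first, a pattern that the year-only bullets repeat. That removes the ambiguity but makes the first bullet govern, with the misplacement shown above. SAP 7.1 does write an explicit otherwise for partial medication dates; these bullets do not. Partial dates should be few, because unsolicited AEs go on a diary card for 28 days after each dose, the card is reviewed at the next visit, and missing data are queried (Protocol 12.1). This limits the size of the problem, not the need for a clear rule.

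**Conclusion.** The point holds as a minor one. (a) The by-dose windows overlap by exactly one day when dose 2 is given on Study Day 29. The overlap involves 0.009 to 1.0 expected events in the HIL-214 arm on the assumed AE rates; the upper end needs all 14 infants dosed that day and the highest rate. The combined subject count does not change. (b) Either bullet in SAP 4 misplaces a substantial share of month-only onsets in dose 2's month, except the second at 56 days. The first can also send them to the listing alone, so that they leave the combined table too. The year-only bullets have the same fault when the doses fall in different years. The shares rest on even onset and calendar spread, and the documents give no count of partial dates.

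Nothing here threatens the trial's conclusions. It is descriptive (SAP 4.1), all AEs are listed, and the rules are the same in both arms. It is worth settling before unblinding because the by-dose tables support a primary endpoint and one infant is a visible share of 14 or 7.

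**What to change.** - **SAP 9.2.** Name one last day for the 28-day period and use it in intervals 1 and 3 and in the listing-only rule. End dose 1's windows at the earlier of that day and the day before dose 2. Assign onsets on or after the dose 2 date to dose 2 only, unless the record shows onset before the injection.
- **SAP 4.** Make the month-only and year-only bullets mutually exclusive, so that the dose-date bullet governs any month (or year) in which a dose was given. Keep the stop-date fallback and add an exception for documented earlier onset.
- **SAP 11.** Record both changes.
- **Dose 2 timing.** Protocol 2.3 and SAP 13.2 footnote (h), Protocol 6.1, Protocol 9.1.6 and SAP 7.2 must be reconciled.

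Cost: a few sentences, a few lines of derivation code, and a wording correction wherever the dose 2 timing changes. No new data are needed.

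Downsides:
- An undocumented onset on the dose 2 day but before the injection, for example after the Visit 2 blood draw, is credited to dose 2.
- About 45%, 21% and under 1% of month-only onsets in dose 2's month (28, 42 and 56 days' spacing) are wrongly credited to dose 2, before any correction from stop dates.
- About 60% of those truly after dose 2 began on Day 8 or later but enter Day 1–7.
- Month-only onsets in the month after dose 2 still go to the 1st. They stay under dose 2, but about 33% of them move from Day 8 or later into Day 1–7.

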#### **9.2.1. Relationship of Unsolicited Adverse Events to Vaccine and Study Procedure**

Relationship to the trial vaccine will also be assessed by the investigator. The relationship of each unsolicited AE to the trial vaccine will be assessed using the following categories:

**Related:** There is suspicion that there is a relationship between the trial vaccine and the AE (without determining the extent of probability); there is a reasonable possibility that the trial vaccine contributed to the AE.

**Not Related:** There is no suspicion that there is a relationship between the trial vaccine and the AE; there are other more likely causes and administration of the trial vaccine is not suspected to have contributed to the AE.

A summary of unsolicited AEs by relationship (i.e. “Related” and “Not Related”) to trial vaccine will be presented in a table by incidence of occurrence. If a subject reports multiple occurrences of the same AE, only the most related occurrence will be presented. AEs that are missing a relationship will be presented in the summary table as “Related” but will be presented in the data listing with a missing relationship. Percentages will be calculated out of the number of subjects in the SAF.

The unsolicited AE data will be categorized and presented by SOC, PT, and relationship up to 28 days after both vaccinations separately.

Relationship to trial procedures should also be determined for all unsolicited AEs. Relationship to trial procedures will be summarized in the same way as relationship to trial vaccine.

#### **9.2.2. Severity of Unsolicited Adverse Event**

A summary of unsolicited AEs by severity will be presented in a table. The severity that will be presented represents the most extreme severity captured on the CRF page. The possible severities are “Mild”, “Moderate”, and “Severe”. In the unsolicited AE severity table, if a subject reported multiple occurrences of the same AE, only the most severe will be presented. Unsolicited AEs that are missing severity will be presented in tables as “Severe” but will be presented in the data listing with a missing severity. Percentages will be calculated out of the number of subjects in the SAF.

The unsolicited AE data will be categorized and presented by SOC, PT, and severity up to 28 days after both vaccinations separately.

### **9.2.3. Serious Adverse Events (SAE)**

The seriousness of an AE should be assessed by the Investigator independently from the severity of the AE. An SAE is defined as any untoward medical occurrence that at any dose results in death, is life-threatening, leads to congenital anomaly/birth defect, requires in-patient hospitalization or prolongation, or results in significant disability/incapacity.

Important medical events that may not result in death, be life-threatening, or require hospitalization may be considered SAEs when, based upon medical judgment, they may expose the subject to danger or may require medical or surgical intervention to prevent one of the outcomes listed above.

SAEs will be presented in a table. At each level of subject summarization, a subject is counted once if the subject reported one or more events. Percentages will be calculated out of the number of subjects in the SAF. The SAE data will be categorized and presented by SOC and PT up to 28 days after second dose and overall.

### **9.2.4. Medically-Attended Adverse Events (MAAEs)**

An MAAE is defined as an AE leading to an unscheduled visit to or by a healthcare professional including visits to an emergency department, but not fulfilling seriousness criteria. MAAEs will be collected throughout the entire study period and will be presented in a summary table for each trial arm and total by SOC and PT up to 28 days after second dose and overall for the SAF.

### **9.2.5. Adverse Events Leading to Trial Vaccine Withdrawal**

A summary of AEs with a study vaccine action taken of “Subject Withdrawn from Subsequent Dose” will be presented in a table. At each level of subject summarization, a subject is counted once if the subject reported one or more events. Percentages will be calculated out of the number of subjects in the SAF. Counts and percentages will be presented by SOC and PT up to the planned time of the second dose administration.

### **9.2.6. Adverse Events Leading to Trial Withdrawal**

A summary of AEs where the answer to “Caused Study Discontinuation” is “Yes” will be presented in a table. At each level of subject summarization, a subject is counted once if the subject reported one or more events. Percentages will be calculated out of the number of subjects in the SAF. Counts and percentages will be presented by SOC and PT up to 28 days after the second dose, and for the overall trial period.

### **9.2.7. Death**

A summary of AEs where the answer to Outcome is ‘Fatal’ will be presented in a table. Percentages will be calculated out of the number of subjects in the SAF.

All subjects who have an AE with an outcome of Fatal will be presented in a listing.

## **9.3. Vital Sign Measurements**

Vital signs are collected prior to each trial vaccine at Visit 1 (Day 1), Visit 2 (Day 29) and at the end of the trial at Visit 4 (End of Trial). These will include heart rate and body temperature.

Vital sign data will be summarized on the SAF by visit for each parameter. All vital sign data will be listed on the SAF.

#### **9.4. Physical Examination**

A complete physical exam will be performed on Day 1, prior to trial vaccine administration. Additional targeted physical examinations may be performed if indicated by review of the subject's medical history. A physical examination includes but is not limited to the following: a check of general appearance, auscultation of heart and lungs, palpation of the abdomen, and inspection of extremities (including skin over the intended injection site). Weight, length and head circumference will also be measured.

Summary tables for physical examinations will be included on the SAF by visit. Weight, length and head circumference will be presented using summary statistics. For other parameters, number and percentages will be presented by abnormality. Physical examination results will be presented in a listing on the SAF.

### **10. Primary Analysis**

Per the protocol, the primary analysis will be performed after the primary safety and immunogenicity data up to 28 days after the last dose (Visit 3) are available. The study database will be monitored, cleaned and locked through the data cut-off time point per data management plan.

### **11. Changes in the Planned Analysis**

- The All Enrolled Set is included for summarizing the screen failures and analysis sets. This set was not defined in the protocol.

## 13. Appendices

### 13.1. Severity Categories for Solicited Safety Parameters

Adverse Event	Severity Grade	Severity
Pain at injection site	0	None
	1	Mild: Minor reaction to touch
	2	Moderate: Cries/protests on touch
	3	Severe: Cries when limb is moved/spontaneously painful
Erythema at injection site (a)	0	$\leq 10$ mm
	1	Mild: $>10 - \leq 20$ mm
	2	Moderate: $>20 - \leq 40$ mm
	3	Severe: $>40$ mm
Induration at injection site (a)	0	$\leq 10$ mm
	1	Mild: $>10 - \leq 20$ mm
	2	Moderate: $>20 - \leq 40$ mm
	3	Severe: $>40$ mm
Swelling at injection site (a)	0	$\leq 10$ mm
	1	Mild: $>10 - \leq 20$ mm
	2	Moderate: $>20 - \leq 40$ mm
	3	Severe: $>40$ mm
Drowsiness	0	Behavior as usual
	1	Mild: Drowsiness easily tolerated
	2	Moderate: Drowsiness that interferes with normal activity
	3	Severe: Drowsiness that prevents normal activity
Irritability/fussiness	0	Behavior as usual
	1	Mild: Crying more than usual/no effect on normal activity
	2	Moderate: Crying more than usual/interferes with normal activity
	3	Severe: Crying that cannot be comforted/prevents normal activity
Loss of appetite	0	Appetite as usual
	1	Mild: Eating less than usual/no effect on normal activity
	2	Moderate: Eating less than usual/interferes with normal activity
	3	Severe: Not eating at all
Vomiting	0	None
	1	Mild: No interference with activity or 1 – 2 episodes/24h
	2	Moderate: Some interference with activity or $>2$ episodes/24h
	3	Severe: Prevents activity, requires outpatient IV hydration
Diarrhea	0	None
	1	Mild: 2 – 3 loose stools/24h
	2	Moderate: 4 – 5 loose stools/24h
	3	Severe: $\geq 6$ watery stools/24h or requires outpatient IV hydration
Fever (b)	Record body temperature in °C/°F	

Abbreviations: h, hour; IV, intravenous.

(a) Subject's LAR to record greatest surface diameter in mm on the diary card.

(b) Fever is defined as body temperature  $\geq 38^\circ$  C ( $100.4^\circ$  F) regardless of method used.

### 13.2. Schedule of Study Procedures

Timing (+allowed window)	Visit 1 Day 1	Post-dose 1			Post-dose 2			
		Phone Contact Day 3	Phone Contact Day 8	Visit 2 Day 29	Phone Contact Day 3	Phone Contact Day 8	Visit 3 Day 29	Visit 4 Day ET
	V1	V1+2 (+2)	V1+7 (+2)	V1+28 (+28)	V2+2 (+2)	V2+7 (+2)	V2+28 (±3)	V2+180 (±10)
Procedure								
Signed informed consent(a)	X							
Assessment of eligibility criteria(b)	X			X				
Assessment of criteria for delay of vaccine administration(c)	X			X				
Demographics(d)	X							
Medical history	X							
Medication/Vaccination history	X			X				
Documentation of trial entrance/Randomization	X							
Physical examination(e)	X			X		X	X	X
Vital signs(f)	X			X			X	X
Blood draw(g)	X			X			X	X
Trial vaccine administration(h)	X			X				
Diary card training(i)	X			X				
Solicited AEs(j)	X	X	X	X	X	X		
Unsolicited AEs(k)	X	X	X	X	X	X		X
Concomitant medications and vaccines(k)	X	X	X	X	X	X		X
Diary card review				X				X
SAEs(l)				Throughout the trial				
MAAEs				Throughout the trial				
AEs leading to trial vaccine withdrawal	X	X	X	X				

AEs leading to withdrawal from trial	Throughout the trial
--------------------------------------	----------------------

